Study clinic visits will be conducted separately from regular medical visits a patient may make at the Hope Center. Subjects will continue to follow-up with their doctors at the Hope Center, schedule their visits through the Hope receptionist, and pick up their medications at the clinic. However, study clinic visits will be conducted by staff employed by the study in physically separate locations from routine medical visits. Study appointments will not conflict with the HIV clinical care that patients receive through coordination between the study receptionist and the clinic receptionist. Study doctors will not provide HIV care or treatment, and subjects will remain enrolled as patients at the Hope Center and receive the same care as prior to enrollment. Before lab tests for the study are performed, confirmation from the subject (and if necessary, the laboratory) will be made to assure no tests, such as Pap smears ordered as standard of care or blood draws, are unnecessarily repeated.

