- After receiving LEEP or cryotherapy, women will be given free condoms and advised to abstain from sexual activities for at least 4 weeks. Women will also be offered an information sheet on the treatment procedure and abstinence information to take home for their spouse or partner. Information includes treatment given, recommended abstinence period and reasons for abstaining from sexual intercourse. These information sheets will be optional to maintain patient confidentiality and safety, especially for people who have not disclosed their status.
- Patients undergoing randomization will have the following performed:

- Blood (10mls) will be drawn to check for HIV viral load and CD4 count
 - Cervix will be swabbed to assess the presence of Human Papillomavirus (HPV) prior to LEEP or cryotherapy
 - Cervix will be swabbed for HIV viral level prior to LEEP or cryotherapy
 - LEEP or cryotherapy performed based on randomization envelope
 - Those undergoing LEEP will have the LEEP piece taken for histology
 - “Randomization” questionnaire completed
 - “Treatment” questionnaire completed
4. First, second, and third-week visits for cervical HIV-1 SHEDDING after treatment (~400 patients) (see Study Flow II)
- Patients who have been randomized and received treatment (approximately 400 patients) will be followed every 1 week for 3 weeks AFTER the treatment intervention to assess healing and measure HIV-1 viral shedding from the cervix. These events can be called the 7-9, 8-10, and 9-11-week visit time points and will probably coincide with the eighth, ninth, and tenth week after enrollment. However, for purposes of measuring HIV viral shedding, it is most important that these time points occur 1, 2, and 3 weeks after the treatment intervention. These terms are consistent and are used for descriptive purposes. They will return 3 times over a 3-week interval and have the following performed:
 - Blood (10mls) will be drawn to check for HIV viral load
 - Cervix will be swabbed to assess the presence of HIV-1
 - “Shedding” questionnaire completed

Shedding information will be considered valid if it is obtained \pm 3 days of the scheduled visit. We will collect shedding information for the first three weeks after treatment but if a patient misses those visits but comes back within six weeks, we will still collect the samples just for comparison purposes.

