If a randomized subject fails to appear for a scheduled study clinic visit then she will be contacted by phone the next day by the receptionist. If the first phone call after a missed visit does not reach the patient or someone who is in contact with the patient, then calls will be repeated at least twice a week for two weeks. If the patient is reached by phone, another visit will be scheduled as soon as possible within one month. If the patient also fails to return for this rescheduled visit, the receptionist will call again the following day. If again the patient does not return for the next rescheduled visit (the third scheduled visit of its kind), or if at least 4 calls have been unsuccessful in reaching the subject, an attempt will be made to visit her at home by a community health worker. If a home visit is unsuccessful in reaching the subject, or if home-visit is successful but the subject fails to return to the study, then she will be considered lost to follow-up (LTFU). If a phone call or home visit reaches the subject, then an appointment will be made for the subject to return to the study clinic. (See Study Tracing Diagram for randomized patients).

Tracing of non-randomized participants

If a non-randomized subject fails to appear for a scheduled visit, including 6-month repeat Pap smear visit after a prior LSIL or CIN1 result she will be contacted by phone the next day by the receptionist. If the phone call does not reach the patient or someone who is in contact with the patient, then a second call will be made the following week. If both calls are unsuccessful in reaching the subject, or if the visit is rescheduled but the subject again fails to show up, then her Coptic Hope file will be flagged, and she will be considered LTFU. If a

phone call or home visit reaches the subject, then an appointment will be made for the subject to return to the study clinic.

Tracing of patients with new QA/QC Cytology results

Both enrolled participants and patients who have been exited from the study may need to be contacted to receive new cytology results based on laboratory QA/QC. Women whose final QA/QC cytology result has been downgraded from the initial result that was disclosed to them, or women whose final results do not require treatment (Normal, ASCUS) will be followed in the same manner as non-randomized subjects: two weekly phone calls and flagged Hope file. These patients will be operationally considered lost at this same point.

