After the checking has been completed, the data manager lists all the corrections that need to be done in the patient charts on the data entry sheet; this helps the data entry clerk easily identify the corrections that need to be done.

Missing values

Restrictions have been put on all questions that are required to be answered. These checks prevent the interviewer from skipping any question that requires a response.

Safety, Security, & Storage

Data security in ODK

- All data collection devices(Tablets) will have a security code for unlocking to prevent unauthorized users
- All the electronic forms will be encrypted before loading to the ODK collect
- The data will be uploaded to Nascop server through a secured path Private key will be used to decrypt the data. ONLY the Data manager will have access to the private key
- Once the data is decrypted , it will be converted into SPSS format.
- All databases are backed up every Friday by saving the most current files on two CD disks and external harddrive and uploaded to the UW-server. All computers are password-protected, preventing access by any unauthorized persons. Data is backed

up on a weekly basis by the data clerk and the data manager. Data is saved on an external hard-drive that remains in the office as well as on a CD that is kept off-site. All data on CD disks will be password protected by the data clerk. All patient records are filed according to numerical order of the patients' identification. Folders are kept in a locked storage cabinet at the study clinic for reference by research personnel. Once the subject completes the study or is lost to follow-up, her records are brought to the KNH office for storage. Participant study ID will be generated by the data manager who will be responsible for linking and de-linking data.

Schedule

Daily

Electronic questionnaire entry – The nurses will complete the forms electronically and upload (send) the data to the ODK server. The data will then be downloaded from the server and saved onto the data computer in SPSS format

Specimen entry – Specimens that are collected in clinic are entered into the *Clinic Specimen CollectionBook*. Results are entered in the *CD4 Results Book*, *Pap Smear Results Book*, and *Biopsy Results Book*.

Laboratory Procedures

Sample collection

- Study nurse will collect Pap smear specimens and cervical swabs for HPV and HIV

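### Failed tracing after any one scheduled visit, weekly shedding visits included, makes a randomised woman lost to follow-up, and the readable text provides no renewed contact for her later recurrence smears

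*Combined protocol and SAP*

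**What the plan says.** **Trigger.** The subsection Tracing of randomized participants opens with the starting condition: "If a randomized subject fails to appear for a scheduled study clinic visit then she will be contacted by phone the next day". No visit type is exempt.

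**Two routes to a home visit.** If she is not reached, calls go on twice weekly for a fortnight, and "if at least 4 calls have been unsuccessful in reaching the subject, an attempt will be made to visit her at home". If she is reached, she is rebooked within a month, and rebooked again if she misses that date. "If again the patient does not return for the next rescheduled visit (the third scheduled visit of its kind"), the home visit follows.

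**End point.** She is lost if the home visit does not find her, and also "if home-visit is successful but the subject fails to return to the study, then she will be considered lost to follow-up (LTFU").

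**The visits covered.** Study Procedures item 4 sets shedding visits at 1, 2 and 3 weeks after treatment for the secondary endpoint. "Shedding information will be considered valid if it is obtained" no more than three days either side of the due date; swabs from late returners, up to six weeks, are taken for comparison only. Item 5 sets the recurrence smears at 6, 12, 18 and 24 months.

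**After loss.** Data Management (Safety, Security, & Storage): "Once the subject completes the study or is lost to follow-up, her records are brought to the KNH office for storage". Statistical considerations for LTFU keeps her in her randomised arm and uses her data up to the point she left.

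**Contrast.** When a non-randomised woman cannot be traced, "then her Coptic Hope file will be flagged, and she will be considered LTFU". For randomised women, Documentation of tracing says only that the loss is passed to the Hope team and social worker to update their files. Yet Study Population & Recruitment says that "subjects will remain enrolled as patients at the Hope Center".

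**The concern.** The primary objective is recurrence over two years, compared by intention to treat at four separate visits (Statistical Methods). A woman absent at Month 6 but present at Month 12 still contributes directly to the later comparisons. The tracing rule instead decides her status in the whole study from the outcome of tracing after one visit, and that visit may serve only the secondary endpoint.

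Loss is also distinct from withdrawal. Withdrawal is recorded on the Exit form, and the Patient Contact form asks whether she wishes to stay. A woman found at home who says she wants to continue, but does not come in, is still coded lost. If nobody calls her when the next smear falls due, usable primary data are given up. Staff are not blinded, and absence soon after a procedure may be related to recovery, so such losses need not be random.

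**Working it through.** **1. The plan's own allowance.** Inputs from Statistical Methods: 4% versus 14%, 80% power, alpha 0.05 (two-sided assumed), 20% loss, 200 per arm. The allowance is 0.20 × 400 = 80 women, 40 per arm.

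Pooled two-proportion formula: n = [1.96√(2 × 0.09 × 0.91) + 0.842√(0.14 × 0.86 + 0.04 × 0.96)]² / 0.10² = 128 per arm. Then 128/0.8 = 160, or 320 in total. With continuity correction: 147, then 184, or 368 in total. Neither gives 400, but 400 errs on the safe side. Power at 4% versus 14%, for one comparison on the women retained:

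| Loss | Per arm | Uncorrected | Corrected | Fisher |
|---|---|---|---|---|
| 20% | 160 | 88% | 84% | 86% |
| 30% | 140 | 84% | 78% | 80% |

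The point therefore concerns avoidable missing data and possible bias more than power.

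**2. Can tracing finish before Month 6?** Month 6 is about day 6 × 365/12 = 182 after treatment. The protocol gives no duration for the home visit and the wait for a return; 14 days is assumed. The one-month limit is stated for the first rebooking and assumed for the second.

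- Week 1 missed, not reached: 7 + 1 + 14 + 14 = day 36.
- Week 1 missed, reached: 7 + 30 + 30 + 14 = day 81.
- Week 3 missed, reached (slowest case): 21 + 30 + 30 + 14 = day 95.

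All end well before day 182. A fortnight of calls also outlasts the three-day validity window, so tracing saves a valid swab only if she is reached almost at once.

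**3. Smears lost per woman if the status is final.**

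| Tracing failed at | Smears lost | Of these, not yet due |
|---|---|---|
| A shedding visit | 4 | 4 |
| Month 6 | 4 | 3 |
| Month 12 | 3 | 2 |
| Month 18 | 2 | 1 |
| Month 24 | 1 | 0 |

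**4. Illustration of visit count.** Assume the same chance q of failed tracing at each visit, independence, and final loss. Cumulative loss is 1 − (1 − q)^k.

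| q | k = 7 (all visits) | k = 4 (smear visits) | k = 3 (shedding visits) |
|---|---|---|---|
| 1% | 6.8% | 3.9% | 3.0% |
| 3% | 19.2% | 11.5% | 8.7% |
| 5% | 30.2% | 18.5% | 14.3% |

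The 20% allowance is reached at q = 1 − 0.8^(1/7) = 3.1% with seven visits, against 1 − 0.8^(1/4) = 5.4% with four. The documents give no value for q.

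**5. Is the status final?** No sentence says so. Storing her records alongside completers' and counting her data only while she was in the study both point that way. The protocol writes return routes for women exited with normal or ASCUS smears and for women with upgraded cytology. The readable text has none for a randomised woman coded lost.

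**The case against.** A reader might infer that one missed visit makes a woman lost. The text does not support that: it takes at least four failed calls or three missed appointments of one kind, and then a home visit that fails or brings no return.

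Nor does one missed swab by itself cost four smears. A woman who misses Week 1 but attends Week 2 or 3 has returned to the study. Someone coded lost around week 5 has missed the whole shedding series.

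The protocol also contains general duties that pull the other way. Item 5 of Study Procedures describes calls and home visits for women lost after randomisation, with weekly discussion. Item 9 says that women who miss appointments are called or visited. The receptionist must bring back those who miss visits, and the shedding section expects some late returners. Folders already travel between the clinic and the KNH office, so where they are kept is weak evidence of status. The tracing diagram for randomised women is not in the text available here, so the absence of later contact is silence in the readable text and not a stated rule.

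These points stand. They rule out the stronger readings. They do not say whether loss can be reversed, or that calls resume when the next smear is due. The six-week provision concerns comparison swabs, not recurrence follow-up.

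**Conclusion.** The concern holds in limited form. Failed tracing after any single scheduled visit, a shedding visit included, makes a randomised woman lost; this can happen before Month 6; and the readable text provides no renewed contact at later smear dates. On the reading that the storage and data rules favour, a woman who has not withdrawn can lose between one and four smears not yet due, depending on when tracing failed before Month 24.

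This rests on finality, which is inferred, and on the diagram adding nothing different. The number of smears that renewed contact would recover cannot be estimated from the documents: any recovery fraction applied to the 80 allowed losses would be a guess, and some losses will be relocation or refusal. A reader might also infer that loss will differ by arm. The unblinded design makes that possible, but nothing in the documents shows it. The change is worth making because it is cheap and protects the Month 6 to 24 intention-to-treat comparisons from avoidable missing data.

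**What to change.** Amend Tracing of randomized participants, Statistical considerations for LTFU, and the record-storage rule:

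1. Code a shedding visit with failed tracing as a missed visit that does not end recurrence follow-up.
2. After failed tracing at Month 6, 12 or 18, code that visit as missed, keep the woman on the calendar, and call again at each later smear date unless she has withdrawn or died. Use an interim status such as *not currently traced* for weekly meetings and DSMB retention reports. Assign final loss only after Month 24 tracing fails.
3. Flag her Hope file, as is done for non-randomised women, and keep her folder available until then.
4. Include smears taken after a gap in the analysis at the visit where they were taken.

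If the tracing diagram already provides for later contact, the text should be brought into line with it.

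The cost is protocol and SOP wording, a few more calls per untraced woman, records kept open longer, and some smears that follow a gap.

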 - Those with biopsy results that are positive for a high grade pre-cancerous lesion (CIN 2/3 or CIS) and if the lesion is amenable to cryotherapy or LEEP as per Kenyan national guidelines, will be eligible for randomization. If they are willing to undergo informed consent for the treatment study, they will be randomized to receive either cryotherapy or LEEP (see Study Flow II). Those who decline to participate in the treatment study will be exited and referred to KNH for treatment. Randomization questionnaire will also be completed during this visit.
 - Those patients who do not have lesions which are amenable to cryotherapy due to size or access will not be randomized but will be offered free LEEP and followed up every 6 months for 2 years, the same way as randomized participants. Those who have lesions that are neither amenable to LEEP nor cryotherapy due to size or severity of disease, or anatomy does not allow proper access to the cervix, will be referred to KNH for subsidized care at this government hospital. The study will not pay for this treatment. Patients will be given follow-up appointments in the study clinic after referral to determine outcomes. They will have the option to continue to be followed at the CCSP.

- Those with CIN 1 will not be randomized or exited but will be asked to return to the study clinic after 6 months for a repeat Pap smear.
- Those who show no dysplasia on histology will be exited from the study and referred to the CCSP for further follow-up.
- It is expected that approximately 400 patients will be eligible for randomization. During randomization, a sealed envelope will be opened by the study doctor that will reveal the randomization arm that has been assigned to the study ID number. Randomization assignment will be performed on a computer by [name], the study statistician, in Seattle, and preparation of the envelopes will be performed by the study data manager in Nairobi in conjunction with [name]. This is the standard used for all randomized clinical trials conducted by the University of Washington in Kenya. Study investigators and the study doctor will not have access to the randomization sequence. Study investigators and staff will not be blinded to randomization.
- Those eligible for randomization will have an HIV cervical viral level swab taken before treatment (LEEP or cryotherapy).

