5. Six, twelve, eighteen, and twenty-four months after randomization visits for RECURRENCE (approximately 400 patients) (see Study Flow II)

- After the 9-11-week visit, randomized participants and those who undergo LEEP but are not randomized because their lesions are not amenable to cryotherapy will return at 6, 12, 18, and 24 months after treatment is administered. At the 24 month visit, the subject will be exited from the study. At these 6-month interval visits, the following will be performed in order:
 - Pap smear to detect recurrence of cervical intraepithelial lesions
 - Same Pap smear swab will be used to assess the presence of Human Papillomavirus (HPV)
 - Blood (5 mls) will be drawn to check for CD4 count
 - “Pap Smear” questionnaire completed
- Pap smear results that are normal, ASCUS, will be filed in the participants file and disclosed at the next scheduled follow-up visit. If pre-cancerous lesions by cytology have recurred then patient will be contacted to return to the study clinic to undergo colposcopic directed biopsy prior to treatment. Results of the colposcopic examination will be entered in the “Colposcopy” questionnaire..
 - If histology-confirmed lesions can be treated by LEEP, then the patient will receive a free LEEP and “Treatment” questionnaire will be filled.
 - If histology-confirmed lesions are too large or cancerous for LEEP then patient will be referred to KNH for subsidized care at this government

hospital. The study will not pay for this treatment. Patients will be given follow-up appointments in the study clinic after referral to determine outcomes.

- Phone calls and home visits will be performed sequentially in the case of a subject who has been lost to follow-up (LTFU) after screening or randomization (see LTFU section). LTFU will be prepared and discussed at weekly clinic meetings. Written reports will be prepared from these meetings and sent to co-investigators. Home visits will be performed by community health workers trained to be discreet in their approach to finding patients. They will not wear clothes that would identify them as health workers and will only use public transportation or unmarked private vehicles. They may ask about the participant's health or whereabouts.

6. Specimen transportation

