Cytology results: Subjects will be notified of their screening cytology results at a study visit scheduled two weeks after their screening visit. If on routine cytology QC re-readings, consensus cytology results are discordant from the initial reading and alternative management is required, subjects will be notified and called back for appropriate follow-up. Subjects with new cytology results of LSIL will be offered colposcopy and biopsy according to 2012 ASCCP guidelines. If the new cytology results are HSIL, ASC-H, or HSIL cannot rule out invasion, patients will be presented with evaluation, treatment and follow-up options, which includes continuation in the study (even if previously exited). Subjects will be given consent information to re-enroll into the study. A Colposcopy form will be completed at this visit. Cytology results from bi-annual follow-up visits for randomized participants and non-

randomized LEEP participants will be disclosed at the next scheduled follow-up visit if the result is Normal or ASCUS. If pre-cancerous or cancerous lesions by cytology have recurred then patient will be contacted to return to the study clinic to undergo colposcopic directed biopsy prior to treatment.

[figure not shown]
Histology results: If the participant needs a biopsy (i.e., HSIL, ASC-H, HSIL cannot rule out invasion, or ICC), they will need to return 4-6 weeks later for histology results. If study staff or a participant feel that having a counselor present at any of these visits would help facilitate the conversation, this can be arranged through utilization of Hope Center counseling staff.

Participants who do not come to their scheduled appointments will be called or visited at home using the contact information provided at enrollment (process described thoroughly below in the Loss to Follow-up & Mortality section).

[figure not shown]
10. Exit

Subjects will exit the study after an interview with the study doctor or study nurse. An “Exit” form will be completed. Participants will be notified that if they wish to know the final results of the study, they may contact the study office 6 months or a year after their participation is complete.

[figure not shown]
Study Flow Diagram I (Enrollment thru Randomization)

Study Flow Diagram II (Randomization thru Exit)

Study Flow Diagram III (Study Tests)

Loss to Follow-up & Mortality

Tracing of randomized participants

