Women whose final results have been upgraded to ASC-H, HSIL, or SCC, and women whose final results are unsatisfactory but had at least one reading of ASC-H, HSIL, or SCC, will receive additional follow-up efforts. This includes at least 6 phone calls over 4 weeks, with at least one call over the weekend. Home visits will also be conducted for these patients when possible. These subjects will be defined as LTFU on a case-by-case basis when all efforts to contact them have been completed.

Tracing of patients with cancer

Any woman who receives an initial or final laboratory result of SCC (cytology) or ICC (histology), whether she is randomized, non-randomized, or exited, will receive the same extensive follow-up efforts as noted above. This includes at least 6 phone calls over 4 weeks, including a phone call over the weekend, and a home visit when possible. These subjects will be defined as LTFU on a case-by-case basis when all efforts to contact them have been completed.

[figure not shown]
Documentation of tracing

All attempts at contacting the patient either through phone call or home visits will be documented in the participant's chart notes. All attempts at home visit will be recorded on the "Patient Contact" form. If a subject is LTFU, this will be recorded on the "Patient Contact" form, in addition to reasons for loss. If a subject withdraws or asks to dis-enroll from the study, the "Exit" form will be completed. If a subject is determined to have died through phone call or home visit, then the "Verbal Autopsy" form will be completed. Information on loss or death will be shared with the Hope clinic team and social worker so that they may update their files.

Statistical considerations for LTFU

Those who are LTFU or dropout after randomization will contribute time and data to the outcomes of measurement for as long as they have remained in the study. They will continue to remain in the arm to which they have been randomized and analyses comparing interventions will include these participants. If, for example, they reach the 6 month time point but did not appear at 12 or 24 months, then data from this subject will be included until 6 months after randomization in a survival analysis. The study coordinator and study doctor will oversee loss and mortality data in coordination with the receptionist.

Study Tracing Diagram for Randomized Participants

Statistical Methods

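### Before randomisation, an original HSIL or ASC-H smear or a CIN 2, CIN 3 or CIS biopsy gets two tracing calls, while the same smear grade reached by re-reading gets at least six calls and, when possible, a home visit

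*Combined protocol and SAP*

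**What the plan says.** Under Tracing of non-randomized participants, a woman who misses a scheduled visit is phoned the next day. If she is not reached, "then a second call will be made the following week". The trigger for loss is "If both calls are unsuccessful in reaching the subject, or if the visit is rescheduled but the subject again fails to show up", and the consequence is "then her Coptic Hope file will be flagged, and she will be considered LTFU". No exception is made for the grade of her result. The next sentence nevertheless refers to a home visit reaching the subject, although none has been prescribed.

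Under Tracing of patients with new QA/QC Cytology results, women whose final re-read result is downgraded, or is Normal or ASCUS, are followed like non-randomised subjects, which that paragraph itself summarises as two weekly calls and a flagged file. A different rule applies to "Women whose final results have been upgraded to ASC-H, HSIL, or SCC" and to women whose final result is unsatisfactory but who had at least one reading of ASC-H, HSIL or SCC. For them, "This includes at least 6 phone calls over 4 weeks, with at least one call over the weekend", with home visits when possible and loss decided case by case. Tracing of patients with cancer gives the same intensive effort to any initial or final SCC smear or invasive cancer on histology, whether the woman is randomised, non-randomised or exited.

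Elsewhere, Study Procedures item 5 provides for tracing by telephone and also states: "home visits will be performed sequentially in the case of a subject who has been lost to follow-up (LTFU) after screening or randomization". Item 9 says "Participants who do not come to their scheduled appointments will be called or visited at home using the contact information provided at enrollment". Item 3 says that women given LEEP without randomisation are "followed up every 6 months for 2 years, the same way as randomized participants".

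**The concern.** Consent for the treatment study and randomisation both take place at the biopsy-result visit. Until then every candidate is non-randomised. She must return twice: for the smear result and colposcopy, then for the biopsy result. At both visits the two-call rule governs a no-show, whatever her smear or biopsy showed.

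Tracing effort for HSIL or ASC-H therefore depends on whether the grade came from the original reading or from a re-reading, and the protocol gives no reason for this. A woman with biopsy-proven CIN 3 awaiting her result is traced no harder than a woman whose re-read smear is normal. A woman with an unsatisfactory final smear and one high-grade reading is traced harder than either.

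Two things are at stake. One is accrual, since these women are the source of the randomised sample. The other is safety, since they have known or strongly suspected high-grade disease that has not yet been treated.

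**Working it through.** **1. The tracing rules side by side** (all from Loss to Follow-up & Mortality)

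| Woman | Effort before she is declared lost |
|---|---|
| Re-read Normal or ASCUS | 2 calls, file flagged |
| Original HSIL or ASC-H, not randomised | 2 calls, or one missed rescheduled visit; file flagged |
| CIN 2, CIN 3 or CIS biopsy, not yet randomised | same as the row above |
| Upgraded to ASC-H, HSIL or SCC on re-reading | at least 6 calls over 4 weeks; home visit when possible; case by case |
| Unsatisfactory final result with one high-grade reading | same as the row above |
| Original or final SCC, or invasive cancer | at least 6 calls over 4 weeks; home visit when possible; case by case |
| Randomised | at least 4 failed calls, or repeated missed visits; then a home visit |

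The second and third rows are out of line with the rest. They carry the results that lead to randomisation, but get the effort assigned to a normal smear.

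**2. Do the other sections supply the missing step?** Items 5 and 9 both mention home visits, but item 5 refers the reader to the LTFU section and item 9 says the process is set out there. That section prescribes no home visit for these women before they are declared lost. The cross-references therefore expose a conflict and do not resolve it. For LEEP women who were not randomised, item 3 points to the randomised rule and the tracing heading points to the two-call rule.

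**3. How much room the plan has.** Inputs: 18% prevalence and 2,400 screened (Statistical Methods); 92 HSIL and 121 LSIL among 500 women (Study Population & Recruitment); about 400 to be randomised.

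- Plan's yield: 0.18 × 2,400 = 432, consistent with the stated approximate 400. From the raw counts, 2,400 × 92/500 = 442.
- Slack against 400: 1 − 400/432 = 7.4%; from 442, 1 − 400/442 = about 9.4%.
- This slack must absorb all loss before randomisation, non-confirmation on biopsy and cryotherapy ineligibility. The 20% allowance in Statistical Methods covers two-year follow-up, not this stage.
- In the other direction, 2,400 × 121/500 = about 581 LSIL women would be offered colposcopy, and some may prove to have CIN 2 or 3. The documents do not say how many.

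**4. What a shortfall would mean for power.** Assume a two-sided 0.05 test, 80% power, 4% versus 14%, and no adjustment for interim looks (sidedness is not stated).

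- n per arm = [1.960 × √(2 × 0.09 × 0.91) + 0.842 × √(0.04 × 0.96 + 0.14 × 0.86)]² / 0.10² = 128.
- Allowing for 20% dropout: 128/0.8 = 160 per arm, 320 in all.
- With continuity correction: 147 per arm; 147/0.8 = 184; 368 in all.

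Neither figure reproduces the stated 400, which is larger than these inputs need. With 400 randomised and 160 per arm completing, power is about 88%. A modest shortfall against 400 would not by itself take power below 80%.

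**5. What cannot be calculated.** The number of women affected is high-grade women × no-show rate × the extra fraction that six calls would recover beyond two. The documents give neither rate, so no figure is put on it.

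**The case against.** The case for treating this as minor has several parts.

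- **The most serious results are covered.** The protocol counts SCC among high-grade smears, and original SCC and invasive cancer already have the intensive rule. A reader might infer that the highest-risk women are lost after two calls. The documents do not support that; the gap concerns HSIL, ASC-H, CIN 2, CIN 3 and CIS.
- **Home visits may have been intended.** Items 5 and 9, and the stray mention in the non-randomised paragraph, point that way. In the re-reading rule, too, the home visit is only when possible. This stands as evidence that the text is inconsistent, but staff following the tracing section would find no home-visit step.
- **Loss is not abandonment.** Results go into the woman's Hope Center file, the flag is put on that file, loss information is shared with the clinic team, and she continues her HIV care there. A reader might infer that known CIN 2/3 is simply left untreated. The text does not say so. These safeguards reduce the risk, but none of them commits anyone to recall her.
- **The groups differ.** Re-read women may already have exited and have no pending visit, whereas original HSIL women have an appointment and travel money. That could explain more effort for the former. It does not explain tracing CIN 3 like a normal re-read.
- **The trial consequence is limited.** Loss before randomisation cannot bias the comparison between arms, screening is set at a minimum of 2,400 and can be extended, and 400 exceeds what 80% power needs. All of this stands.

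**Conclusion.** The inconsistency is real and should be corrected. As written, women with an original HSIL or ASC-H smear, or with CIN 2, CIN 3 or CIS awaiting randomisation, get the weakest tracing rule in the protocol. The same smear grade reached by re-reading gets at least three times as many calls (six against two) and a possible home visit. The tracing section also disagrees with Study Procedures items 3, 5 and 9 and with its own mention of a home visit.

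The consequence is for accrual and for the safety of women with untreated high-grade disease. It is not a threat to the validity of the arm comparison, and power is not the main issue. The slack of about 7% (432 against 400) assumes the plan's 18% prevalence and 2,400 screened. It takes no account of non-confirmation or ineligibility, which shrink it, or of LSIL women found to have CIN 2 or 3, who enlarge it. A reader might want to turn this into a percentage of the randomisation target lost. That would need no-show and recovery rates the documents do not give. It would also have to leave out women whom two calls would bring back and smears that never lead to randomisation.

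**What to change.** In Tracing of non-randomized participants, limit the two-call rule to women whose current result needs no further study procedure. Add that a woman not yet randomised who has an original HSIL or ASC-H smear, or a CIN 2, CIN 3 or CIS biopsy, and who misses a results, colposcopy or randomisation visit is traced by the rule already written for upgraded smears: at least six calls over four weeks, and a home visit when possible. Leave the cancer paragraph as it is.

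Then reconcile this section with Study Procedures items 3, 5 and 9, so that each says the same about home visits, and state explicitly which tracing rule applies to LEEP participants who were not randomised.

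The cost is a protocol and SOP wording change, plus some extra calls and home visits by the receptionist and community health workers already employed. It needs no new procedure, form or analysis.
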